### **Missing or partial end date:**

Imputation will be performed for the end date only if the day or month is missing (i.e., year is present):

- If month and day are missing, then assign December 31
- If only day is missing, then assign the last day of the month

If the imputed start date is later than the imputed end date, then set the imputed start date to the imputed end date.

Prior and concomitant medications will be coded using the World Health Organization - Drug Dictionary Enhanced (WHO-DDE) and summarized by Anatomical Therapeutic Chemical (ATC) drug class, preferred term (PT) and by treatment group, total olezarsen treated and overall based on the Safety Set. Actual versions of WHO-DDE used will be stated in the clinical study report.

The number and percentage of patients in each of the following categories will also be summarized by treatment group, total olezarsen treated, and overall using the Safety Set:

- Not taking statins at baseline
  - Initiated statins after study drug administration
  - Taking statins at baseline
- Increased statin dose or switched to higher intensity after study drug administration

All prior and concomitant medications will be listed based on the Safety Set.

## 4.9 Efficacy Evaluation

The primary endpoint will be assessed on the FAS and PPS, with the former being the basis for the primary efficacy analysis. All the secondary endpoints will be assessed on the FAS.

#### 4.9.1 Analysis and Data Conventions

##### 4.9.1.1 Hypothesis

The null hypothesis of the primary analysis is that there is no difference between olezarsen and Placebo in the percent change in fasting TG from Baseline at Month 6. The alternative hypothesis is that there is a difference between olezarsen and Placebo in the percent change in fasting TG from Baseline at Month 6.

Symbolically, this is expressed as follows:

$$H(0) : \mu(\text{test}) = \mu(\text{reference})$$

$$H(1) : \mu(\text{test}) \neq \mu(\text{reference})$$

##### 4.9.1.2 Multi-center Studies

The term 'Center' will be used to define each investigator site. The study will be conducted at multiple centers in multiple countries. The data from all study centers will be pooled together for the statistical summaries.

##### 4.9.1.3 Adjustments for Covariates

The covariate will include the baseline stratification factor and baseline measurements.

The baseline stratification factor will be classified as two categories below based on the base TG

- Baseline TG  $\geq$  500 mg/dL (5.65 mmol/L) vs.  $<$  500 mg/dL

##### 4.9.1.4 Handling of Dropouts or Missing Data

#### **Multiple imputation for missing fasting TG at month 6 and/or month 12:**

As the randomization stratification factor, the fasting TG at qualification visit will not be missing. Therefore, the baseline fasting TG for all randomized patients will not be missing as the fasting TG at qualification visit will be used to calculate the baseline fasting TG (refer to Section 4.2.2).

Patients with a missing fasting TG at Months 6 and/or 12 will have missing values multiply imputed based on the known assessments from the retrieved dropouts (e.g., for Month 6, the retrieved dropouts include those patients who discontinue treatment before Week 25 but still have assessments at Week 25 or 27; for Month 12, the retrieved dropouts include those patients who discontinue treatment before Week 51 but still have assessments at Week 51 or 53), if there are a sufficient number of retrieved dropouts. The imputation model contains the following variables: baseline fasting TG, fasting TG at each post-baseline visit and the multiple imputation will be stratified by treatment group (Schafer 1997; Schafer 1999).

If there is no sufficient number of retrieved dropouts, missing TG value after treatment discontinuation at Month 6 or Month 12 will be imputed using a "wash-out" (Jump to Reference, J2R) multiple imputation approach. With the approach, patients treated with olezarsen who discontinue treatment will have missing TG values after the last "observed value" multiply imputed based on baseline fasting TG and the imputation model for the placebo group. Patients in the placebo group who discontinue the treatment will have missing TG values multiply imputed using the baseline fasting TG, fasting TG values at post-baseline visits from the placebo group.

The Markov Chain Monte Carlo (MCMC) method will be used under the multivariate normality assumption to impute the missing values by treatment group. The variable list for imputations will include the baseline value, as well as all available post-baseline value. To conform to the multivariate normality assumption, baseline and post-baseline fasting TG will be natural log-transformed before the imputation process, the data will be back transformed to create the imputed data set after the imputation. The SAS procedure PROC MI will be used to create 1000 imputed datasets. The first 100 imputed datasets with imputed values within the analytical measuring range will be chosen from 1000 imputed datasets for the analysis.

Default EM algorithm will be used to derive a set of initial parameter estimates for MCMC method. A non-informative prior (Jeffreys' prior) will be used to derive the posterior distribution of the parameters.

The following pseudo SAS code and seed (2438291) will be used to perform the multiple imputation:

Step 1, using PROC MI to generate 1000 imputations:

```

/*****
/* Note:
/* baseline = baseline fasting TG
/* impute = the iteration number in the multiple imputation
/* trtpn = Treatment group: 0=Placebo, 1= olezarsen 50 mg, 2 = olezarsen 80 mg*/
*****/

proc mi data = TG seed = 2438291 nimpute = 1000 out=TGIM;

    transform log(baseline) log(week5) log(week9) log(week13) log(week17)
    log(week21) log(month6) log(week29) log(week37) log(week45) log(month12);

    mcmc;

    var baseline week5 week9 week13 week17 week21 month6 week29 week37 week45
    month12;
    by trtpn;

run;

```

Step 2, extract placebo data, fit a GLM model using log transformed data for each imputation and get parameter estimates:

```

proc glm data=pla_mar;
    by paramcd imputation_;
    model AVAL_log=base_log avisitn_interval/solution;

run;

```

Step 3, for patients in the active arm, remove the imputed data post last "observed value", apply the parameter estimates calculated from step 2 to active treatment arms and back transformed the data to create the 1000 imputation datasets.

Step 4: Set the dataset from step 3 and the subset of placebo dataset (the dataset used in step 2) together then choose the first 100 imputation dataset with imputed values within the analytical measuring range.

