### 5.1 Inclusion Criteria

1. Must have given written informed consent (signed and dated) and any authorizations required by local law and be able to comply with all study requirements
2. Aged  $\geq 18$  years at the time of informed consent
3. Fall into at least 1 of the following groups (a or b):
  - a. Hypertriglyceridemia with fasting TG  $\geq 150$  mg/dL (1.69 mmol/L) and  $< 500$  mg/dL (5.65 mmol/L) with either
    - Clinical diagnosis of ASCVD defined as documented coronary artery disease (CAD), cerebrovascular disease, or peripheral artery disease ([Appendix F](#)), or
    - At increased risk for ASCVD defined as:
      - Type 2 Diabetes mellitus, or
      - Two (2) or more of the following cardiovascular (CV) risk enhancing factors:
        - Men  $\geq 55$  years of age or women  $\geq 65$  years of age
        - Women with a history of preeclampsia, or premature menopause (before the age of 40 years)
        - Family history of premature ASCVD (before the age of 55 years for males, or before the age of 65 years for females)
        - Current tobacco use (5 cigarettes/day or more for at least 1 year)
        - Metabolic syndrome (see [Appendix F](#) for definition)

- Hypertension requiring antihypertensive treatment
- Chronic kidney disease stage 3 or (eGFR 30-59 mL/min/M)
- LDL-C  $\geq$  160 mg/dL
- LDL-C  $\geq$  100 mg/dL on therapy to lower LDL-C
- Elevated high-sensitivity C-reactive protein ( $\geq$  2.0 mg/L)
- Elevated lipoprotein (a) ( $\geq$  50 mg/dL or 125 nmol/L)
- Ankle brachial index  $<$  0.9 in asymptomatic patients
- Coronary artery calcium score  $\geq$  100

b. Severe hypertriglyceridemia with fasting TG  $\geq$  500 mg/dL (5.65 mmol/L)

**Note:** TG levels must meet inclusion criteria at both the Screening Run-In Visit and the Screening Qualification Visit. If the fasting TG is below the required level at a Visit, up to 2 additional tests may be performed with the average of the tests used to consider eligibility at that Visit.

4. Patients should be on standard of care (SOC) lipid-lowering medications per local guidelines ([Appendix E](#)). Lipid-lowering medications should be optimized and stabilized for at least 4 weeks prior to Screening to minimize changes in these medications during the study. Patients taking over-the-counter (OTC) omega-3 fatty acids should make every effort to remain on the same brand through the end of the study

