### **8.5.7 Safety Monitoring for Triglyceride and Apolipoprotein B Elevations**

Triglycerides (TG) will be monitored for safety every 3 months. If the measured triglyceride level either (a) in patients with Baseline TGs < 500 mg/dL subsequently exceeds 880 mg/dL or (b) in patients with Baseline TGs  $\geq$  500 mg/dL and < 2000 mg/dL subsequently exceeds 2000 mg/dL and increases by at least 10% from Baseline or (c) in patients with Baseline TGs  $\geq$  2000 mg/dL subsequently increases by at least 30% from Baseline, the site will be notified to contact the patient by phone as soon as able, and no later than their next monthly visit or phone call, to counsel the patient on dietary, lifestyle and medication compliance, and educate and assess the patient for signs and symptoms of pancreatitis. To maintain the blind, the same notification will be provided for an additional patient in the other treatment group using pre-defined criteria to balance the frequency of alerts for both treatment groups, active and placebo. If the TG value remains persistently high at the next regularly scheduled TG safety assessment, a qualified individual, ideally not associated with that subject's assessment, will be informed of the TG value to evaluate and manage the patient's TG levels, moving forward throughout the study, ideally independent of the Investigator's and Study Coordinator's knowledge.

Given the potential for LPL inhibition to change the distribution of cholesterol on lipoproteins, without necessarily affecting the number of cholesterol-rich lipoproteins, apoB levels rather than LDL-C levels will be monitored for safety at 6 months then every 3 months, consistent with guidelines which recognize apoB as the optimal atherogenic lipid metric ([Mach et al. 2020](#)). If the measured apoB level increases by  $\geq$  20 mg/dL, the site will be notified to counsel the patient at their next monthly visit on lifestyle and medication compliance. To maintain the blind, the same reminder will be provided for an additional patient in the other treatment group, using pre-defined criteria to balance the frequency of alerts for both treatment groups, active and placebo. If the subsequent measurement is still high, then the Investigator will be informed of the apoB value and if clinically indicated based on local SOC, may adjust background lipid lowering therapy, in consultation with the patient, according to patient's ASCVD risk.

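### SAP 4.9.1.4 discards whole imputed datasets when an imputed TG value falls outside an unstated assay range, so Rubin's rules are applied to imputations selected on their outcome

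*Combined protocol and SAP*

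**What the plan says.** SAP 4.9.1.4 imputes missing fasting TG on the log scale, after which "the data will be back transformed to create the imputed data set after the imputation". The call is "proc mi data = TG seed = 2438291 nimpute = 1000 out=TGIM", with no minimum or maximum option. The text then sets the retention rule: "The first 100 imputed datasets with imputed values within the analytical measuring range will be chosen from 1000 imputed datasets for the analysis". Step 4 repeats it once the placebo and olezarsen data have been put back together: "choose the first 100 imputation dataset with imputed values within the analytical measuring range". The other lipids follow a similar Step 4.

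If there are too few retrieved dropouts, missing olezarsen values are "multiply imputed based on baseline fasting TG and the imputation model for the placebo group" (jump to reference), so the same rule acts on placebo-like draws in the active arms.

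On the population, Protocol 5.1 admits "Severe hypertriglyceridemia with fasting TG" of 500 mg/dL or more, with no ceiling. Protocol 8.5.7 has an alert rule "in patients with Baseline TGs $\geq$ 2000 mg/dL subsequently increases by at least 30% from Baseline", which starts at 2000 × 1.3 = 2600 mg/dL. SAP 4.11.3.3 counts post-baseline TG above 2000 mg/dL as an exploratory category.

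The documents give no measuring range. They do not say whether the check covers Month 6 and Month 12 only or all ten post-baseline variables in the imputation model. They give no instruction for a yield below 100.

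**The concern.** Rubin's rules combine draws from a posterior predictive distribution. Keeping a draw only if all of its values lie in a range conditions the set on the outcome being imputed. An upper limit preferentially removes datasets in which severe patients with missing data have high TG, while observed patients with equally high TG remain. A lower limit would remove low draws in the same way.

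Two things are at stake. The first is operational. The seed and the number of imputations are fixed, and fewer than 100 may qualify. Because imputation runs by treatment group, a shortfall in the real data would appear only after unblinding, and the primary analysis would then need an unplanned change. The second is statistical, because the selected datasets feed the Month 6 and Month 12 TG analyses, the TG responder analyses, and the Wilcoxon, tipping-point and log-ratio sensitivity analyses. No planned analysis repeats the primary imputation without the filter.

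**Working it through.** The plan gives no figure for the expected yield, so there is none to reproduce. The planned effect (60 points) and SD (73%) in Protocol 10.2 serve as the yardstick. With 33 v 22 patients the standard error is 73 × √(1/33 + 1/22) = 20.1. That gives power Φ(60/20.1 − 1.96) ≈ 85% (83% by noncentral t) against the stated 80%. The difference is on the safe side and does not bear on this point.

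**Inputs from the documents.** 152 patients at 1:1 and then 3:1 give 57, 57 and 38. Dropout is 20%, about 30 patients. SD of percent change is 73%, with no mean change on placebo.

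**Assumptions.** Upper limit U of 1000 to 5000 mg/dL. Imputed TG = baseline × log-normal ratio. Case (a): log-SD s = √ln(1 + 0.73²) = 0.65 with mean ratio 1, so μ = −s²/2 = −0.21. Case (b): s = 0.40 with median ratio 1, so μ = 0. Month 6 and Month 12 values are checked, with within-patient correlation 0.6.

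**Step 1: chance that one patient passes.** One value passes with probability Φ(z), where z = (ln(U/baseline) − μ)/s. For baseline 2000 and U = 2000 this is 0.628 in (a) and 0.500 in (b). Both values pass with the bivariate normal probability at z: 0.489 in (a), and 1/4 + arcsin(0.6)/(2π) = 0.352 in (b).

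**Step 2: yield out of 1000.** The required 100 needs a pass probability of at least 0.10. Counting only the severe patients with missing data, and treating them as independent:

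| Missing severe patients | U = 2000 | U = 2600 | U = 5000 |
|---|---|---|---|
| One, baseline 2000 | 352–489 | 627–656 | 928–980 |
| Two, baseline 2000 | 124–239 | 393–430 | 862–961 |
| Three, baseline 2000 | 44–117 | 247–282 | 800–942 |
| Two, baseline 3000 | 5–59 | 50–157 | 624–702 |

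For example, three patients at U = 2000 in (b) give 0.352³ = 0.044, or 44 datasets. At U = 1000, a simulation with one missing patient at baseline 2000 among the 30 gives 12–78. With no severe patient missing, 984 or more pass at U = 2000. If five visits per patient are checked instead of two, two patients at baseline 2000 give 41–100 at U = 2000, so the unstated scope can decide whether the rule works. No scenario tried fell short at U = 5000.

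A fuller placebo-arm simulation, with 10–25% of patients assumed severe, puts the chance of fewer than 100 qualifying at 25–57% (U = 1000), 3–17% (2000), 0–7% (2600) and 0% (5000).

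**Step 3: truncation of the mean.** With c = U/baseline, the retained mean ratio is exp(μ + s²/2) × Φ(z − s)/Φ(z), where z = (ln c − μ)/s. For baseline 2000 and U = 2000:
- (a) 1.000 × 0.372/0.628 = 0.592, a fall of 41 points
- (b) 1.083 × 0.345/0.500 = 0.747, a fall of 34 points

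The corresponding falls are 21–31 points at U = 2600 and 2–10 at U = 5000. For a baseline of 260 the fall is 0.2 or less at U = 2000 and above.

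**Step 4: arm level.** One such patient at U = 2000 moves the placebo mean by 34/38 to 41/38 = 0.9 to 1.1 points, or an olezarsen mean by 34/57 to 41/57 = 0.6 to 0.7. Simulation of all missing values in an arm gives:
- Placebo, U = 2000, one missing patient at baseline 2000 to 2500: 0.9 to 1.6
- The same at U = 2600: 0.55 to 1.2
- One missing patient at baseline 700 per arm, U = 2000: 0.24 or less
- Largest value seen, at U = 1000: 3.25

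With 57 v 38 patients the standard error from the planning SD is 73 × √(1/57 + 1/38) = 15.3, so 1.6 points is about 0.10 standard errors.

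**The case against.** The strongest reply is that the deciding figure is absent and the plan's own use of the assay suggests a wide range. Alerts in Protocol 8.5.7 act on measured TG above 2000 mg/dL, and from 2600 mg/dL for the highest baselines. On that view the rule would rarely bind. This stands, and it makes the U = 1000 and U = 2000 rows the less likely ones. It does not show that 2600 mg/dL is well inside the range used for filtering, and the plan does not say so.

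Also fair: discontinued patients are strongly encouraged to attend Weeks 25, 27, 51 and 53 (Protocol 8.7.1), so missing TG may be below 20%. The completer analysis (SAP 4.9.2.2, Sensitivity Analysis 2) is untouched by the filter. If Step 3 applies the regression estimates without residual draws, olezarsen values would leave the range less often than modelled. A shortfall could be met by generating more imputations, with the deviation documented as SAP section 1 allows.

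A reader might infer three stronger things, none supported by the documents:
- **That the primary analysis will fail.** This needs a low limit, or several missing patients with baselines near or above it.
- **That only the placebo tail is cut, biasing the result one way.** Jump-to-reference olezarsen values are cut too. A lower placebo mean shrinks the apparent effect and a lower olezarsen mean enlarges it.
- **That the standard error is materially understated.** The effect on between-imputation variance depends on the simulation set-up. One gave ratios of 0.5–0.9 when the filter binds; another gave ratios near 1 from U = 2000 up. Neither was carried through to a total standard error.

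**Conclusion.** The point holds as a defect of method whose size is conditional. That the rule is stated twice, acts on whole datasets after the arms are combined, and selects imputations on their outcome follows from the text alone. Its practical effect rests on an assumed limit, baselines and log-normal spread. It is negligible at about 5000 mg/dL or more. At about 1000 to 2600 mg/dL there is a possible shortfall below 100 datasets and a small arm-level shift in either direction. Against a planned difference of 60 points the primary conclusion is unlikely to change. For the other lipids no size can be given, because neither their ranges nor their spread is stated.

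The change is still worth making before unblinding. If the range is wide the filter does nothing useful; if it is narrow it can distort or stall the primary analysis.

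**What to change.** In SAP 4.9.1.4, delete the dataset-level filter from the text and from Step 4, and analyse the first 100 imputations as generated. Do the same for the other lipids. If the filtered version is wanted, keep it only as a sensitivity analysis that states the range and the visits checked and reports the number of datasets rejected.

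If limits on implausible values are still wanted, pre-specify fixed per-value limits wide enough to cover all observed TG values. Apply them both to the PROC MI draws and to the values created in Step 3; PROC MI bounds alone would not reach the latter. Report how many values were affected.

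The cost is SAP wording and a small code change, with no effect on trial conduct. The downside is that an occasional large imputed value may slightly widen the confidence interval.

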#### **8.7.1 Follow-up Visits for Early Termination from Treatment Period or Post-Treatment Follow-up Period**

If a patient discontinues early from the Treatment Period, treatment early termination (Tx-ET) visit assessments should be performed 4 weeks from the last dose of Study Drug, and patients should start the 13-week Post-Treatment Follow-up Period to collect the study assessments in accordance with the Schedule of Procedures in Appendix A. Patients should also be strongly encouraged to attend remaining landmark visits at Weeks 25 and 27, as well as at Weeks 51 and 53 (calculated based on the time elapsed since Day 1) to collect fasting lipid panels and conduct safety assessments in accordance with Appendix A. Depending on the day of discontinuation, follow-up visits and landmark visits may overlap and can be combined.

Any patient who chooses to discontinue early from the Post-Treatment Follow-up Period should be strongly encouraged to complete safety procedures and observations in accordance with Appendix A. If the patient declines or is unable to participate in the above, final post-treatment

early termination (Post-Tx ET) assessments should be performed at the time of withdrawal in accordance with [Appendix A](#).

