## **4.13 Changes to Protocol-planned Analyses**

In protocol, it states: 'All primary and secondary endpoints will be assessed on the FAS and PPS, with the former being the basis for the primary efficacy analysis.' The secondary endpoints on PPS will not be assessed in this SAP.

In protocol, it states: The missing TG value at Months 6 or 12 will be imputed using an imputation model that contains the following variables: baseline fasting TG, fasting TG at each post-baseline visits and the multiple imputation will be stratified by treatment group ([Schafer 1997](#); [Schafer 1999](#)). The missing value imputation method for the primary analysis is updated in the SAP as below:

The retrieved dropouts multiple imputation approach will be used for imputing missing values after discontinuation for the primary efficacy analysis. If there is not a sufficient number of retrieved dropouts, a placebo washout multiple imputation approach will be used for imputing missing values for the primary efficacy analysis.

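### In the SAP's fallback imputation, Step 3 is keyed to the last observed triglyceride value and not to treatment discontinuation, so it contradicts the prose and mishandles two kinds of missing value

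*Combined protocol and SAP*

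**What the plan says.** SAP 4.9.1.4 imputes missing fasting TG at Months 6 and 12 by one of two routes. The first uses retrieved dropouts and is introduced in general terms: "Patients with a missing fasting TG at Months 6 and/or 12 will have missing values multiply imputed". The second is a fallback, used "If there is no sufficient number of retrieved dropouts"; the SAP does not say what number is enough.

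The fallback prose opens with its scope: a "missing TG value after treatment discontinuation at Month 6 or Month 12 will be imputed using a" jump-to-reference (J2R) approach. The sentence that carries it out says that "patients treated with olezarsen who discontinue treatment will have missing TG values after the last" observed value imputed from baseline TG and the placebo model.

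The pseudo-code is the only TG imputation code given. In Step 1 the MCMC method "will be used under the multivariate normality assumption to impute the missing values by treatment group", with no variable for being on or off treatment. Step 2 fits a model to the placebo data. Step 3 then says "for patients in the active arm, remove the imputed data post last" observed value, and the Step 2 estimates are applied to the active arms. SAP 4.9.1.4 reuses Steps 2 to 4 in similar form for the nine other lipids.

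Protocol 8.7.1 says that patients who stop treatment early should be "strongly encouraged to attend remaining landmark visits at Weeks 25 and 27, as well as at Weeks 51 and 53". SAP 4.2.3 maps those values to analysis visits. SAP 4.9.2.1 applies a treatment-policy strategy to discontinuation.

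**The concern.** Under a treatment-policy estimand, a value missing after a patient has stopped drug should be imputed as off drug, and a value missed while on drug as on drug. The last observed value does not make that distinction, for two reasons.

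1. Step 3 covers the whole active arm. A patient still being dosed who has no later lipid value is imputed from placebo. The prose would not do this, so two programmers, one working from the prose and one from the code, would build different datasets.
2. A value missing after discontinuation but before a later observed value is not removed by Step 3. It keeps the Step 1 draw, made within the patient's own arm under missing at random (MAR). The operative prose sentence starts at the same point, so prose and code share this fault, although the opening sentence of the fallback would cover such a gap.

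The two errors have opposite signs. The second can reach the Month 6 primary endpoint. The first bears mainly on Month 12 TG, which heads the secondary testing sequence in SAP 4.9.1.5.

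**Working it through.** The plan gives no figure on this point. The check has two parts: apply the rules to each missing-data pattern, then size the shift from the planning inputs.

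**Part 1: patterns in an olezarsen patient.** The alternative rule uses placebo-based draws for values missing after discontinuation and own-arm draws otherwise.

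| Pattern | Time point | Step 3 as written | Keyed to discontinuation |
|---|---|---|---|
| On drug, only Month 12 missing | Month 12 | placebo | own arm |
| On drug, Month 6 missing, later values present | Month 6 | own arm | own arm |
| On drug throughout, no value after Week 21 | Months 6 and 12 | placebo | own arm |
| Stopped after Week 13, nothing later | Months 6 and 12 | placebo | placebo |
| Stopped after Week 13, values to Week 21, then none | Months 6 and 12 | placebo | placebo |
| Stopped after Week 13, Month 6 missed, Month 12 observed | Month 6 | own arm | placebo |
| Stopped after Week 13, Month 6 missed, Week 29 observed, then none | Month 6 | own arm | placebo |

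The rules differ in rows 1, 3, 6 and 7. Rows 1 and 3 arise from the code alone. Rows 6 and 7 arise from the code and from the operative prose sentence.

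**Part 2: size.** Inputs:
- 152 patients, 1:1 to cohorts and 3:1 within cohort (Protocol 4.2): 152/2 × 0.75 = 57 per olezarsen arm and 152 × 0.25 = 38 pooled placebo.
- A 60% reduction on olezarsen, no change on placebo, SD about 73% (Protocol 10.2).
- The numbers of patients below are assumptions; the documents give none.

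*On drug, imputed as placebo.* Shift per patient = 60/57 = 1.05 points toward no effect. For 1, 3 and 6 such patients: 1.1, 3.2 and 6.3 points.

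*Off drug, Month 6 missed, later value observed.* Step 1 conditions on the later value. Assume that Month 12 is back at baseline, that the on-drug log ratio is ln(0.4), that the log-scale variances at the two time points are equal, and that their correlation is ρ. The imputed Month 6 change is then about exp[(1 − ρ) × ln(0.4)] − 1, against 0 under J2R:

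| Assumed ρ | Imputed Month 6 change | Shift per patient (change/57) |
|---|---|---|
| 0.3 | −47.3% | 0.83 |
| 0.5 | −36.8% | 0.65 |
| 0.7 | −24.0% | 0.42 |
| 0.9 | −8.8% | 0.15 |

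Two such patients shift the arm mean by 2 × 0.15 = 0.3 to 2 × 0.83 = 1.7 points toward olezarsen. The calculation leaves out the patient's early on-drug values, which would pull the draw back toward −60%. The ceiling is 1.05 points per patient.

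*Scale.* The standard error of the arm difference, ignoring covariate adjustment, is 73 × √(1/57 + 1/38) = 15.3 points. A shift of 3.2 points is 0.21 of that and 1.7 points is 0.11.

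**The case against.** The strongest reply has five parts.

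**It is only a fallback.** True, and the point holds only when J2R is used. It may well be used: at 20% dropout (Protocol 10.2), about 0.20 × 57 = 11 patients per olezarsen arm drop out. If treatment discontinuation is similar, retrieved dropouts are only part of that number, and the Step 1 variable list has 11 variables.

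**The prose governs the pseudo-code.** If so, the on-drug error disappears. The conflict still has to be resolved, and J2R would then leave no stated rule for values missed on treatment in the fallback. The gap error remains under either reading.

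**The on-drug error barely touches the primary endpoint.** This stands. At Month 6 it needs a patient on drug with no lipid value from Week 25 onward. Even at Month 12, one of the two visits is enough (SAP 4.2.2).

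**Off-drug returners will be few.** This largely stands. A reader might infer that the protocol invites patients to skip Month 6 and return at Month 12, but Protocol 8.7.1 encourages all landmark visits. By scheduled days, stopping after a last dose at Week 9, 13, 17 or 21 puts a treatment-termination or follow-up visit on day 176, 169, 169 or 169, inside the Week 25 window of days 156 to 176. SAP 4.2.3 does not say clearly whether such follow-up visits are mapped.

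**Sensitivity analyses cover it.** The completer and tipping-point analyses (SAP 4.9.2.2) do probe reliance on imputed values. The tipping-point shift is a constant over an arm's imputed values, so it does not separate on-drug from off-drug gaps.

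Two further inferences are not supported. SAP 4.13 might be read as restricting placebo-based imputation to values missing after discontinuation, but its sentence "approach will be used for imputing missing values after discontinuation for the primary efficacy analysis" describes the retrieved-dropout approach; the washout sentence after it has no such limit. The copy-increment-from-reference (CIR) analyses in Sensitivity Analysis 5 might be thought to share the on-drug error, but they are limited to patients who discontinue treatment. They share only the start point at the last observed value.

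**Conclusion.** Step 3 is wrong as written, not merely short of detail. It contradicts the prose on who receives placebo-based draws. Prose and code together also leave own-arm draws in gaps that follow discontinuation and precede a later value.

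The on-drug error costs up to 1.05 points per patient toward no effect, mainly at Month 12. The gap error costs about 0.2 to 0.8 points per patient toward olezarsen at Month 6. Both rest on the planning effect of 60 points and 57 patients per arm. The second also rests on Month 12 being back at baseline and on assumed correlations of 0.9 to 0.3. The net effect depends on attendance patterns that the documents do not give.

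A reader might infer that the code simply swaps on-drug and off-drug patients, with a full 60-point error each way. That is too strong: off-drug returners are not imputed fully as on drug, because Step 1 uses their later values. Nor do the figures support a claim that the primary conclusion would reverse. The shifts illustrated are small against a 60-point effect and a standard error of about 15 points. The case for change is that the rule is ambiguous in the fallback for the primary analysis and cheap to correct.

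**What to change.** In SAP 4.9.1.4:

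- Key Step 3 to recorded treatment discontinuation. The protocol's own end of treatment, one 4-week dosing interval after the last dose (Protocol 6.1.2 and Appendix A), would serve as the date.
- Apply placebo-based draws only to olezarsen values missing after that date, including gaps before a later observed value.
- State that values missed while on treatment are imputed within arm under MAR.
- Align the operative prose sentence with this, and carry the rule into the imputation of the other lipids.

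In Sensitivity Analysis 5 (SAP 4.9.2.2), change only the start point of the CIR imputation, from the last observed value to discontinuation. Protocol 10.6.3.1 already starts it there.

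The cost is one flag in the analysis dataset, from dosing dates already collected, and a modest programming change. One consequence should be accepted openly: a J2R draw in a gap uses baseline TG and the placebo model, and ignores the patient's later off-treatment value. Conditioning on that value would be a different model and is not needed for this correction.
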